LY900018: Single 3-mg dose; nasal administration by study site personnel IMG (GlucaGen, Novo Nordisk A/S): Single 1-mg dose; IM injection by study site personnel Patients will undergo a screening examination within 28 days prior to enrollment. Patients will be administered a single dose in Periods 1 and 2, which will be separated by a washout period of 3 to 14 days. Patients will return for a follow-up visit 26 to 30 days after the last study treatment.

Number of Patients:

Seventy five patients may be enrolled in order to have at least 66 patients (at least 30 patients with T1DM and T2DM, respectively) complete both periods with evaluable primary outcome. If patients discontinue from the study before completion of both periods with evaluable primary outcome for any reason, the patient may be replaced. Replacement should not occur beyond 75 patients enrolled, if it is expected to have at least 66 patients complete the study.

Statistical Analysis:

A total of 66 completers are required in the study in order to achieve the primary objective with at least 90% power using the following assumptions:

- A treatment success rate of 98% for both treatments
- A non-inferiority margin (NIM) of 10%
- One-sided alpha level of 0.025
- A within-patient correlation of zero between 2 treatment visits

The primary analysis will be a treatment comparison of the percentage of patients, including both T1DM and T2DM, who achieve treatment success. The percentage of patients who achieve treatment success within each treatment group and the difference in the percentages between the 2 treatment groups will be computed. A 2-sided 95% confidence interval (CI) will be obtained from the 1-sample mean of the paired differences in primary outcome (1=outcome observed; 0=outcome not observed) across 2 treatment visits. Non-inferiority of LY900018 will be declared if the upper limit of the 2-sided 95% CI constructed on the difference in percentage (IMG - LY900018) is less than the NIM of 10%.

2. Schedule of Activities

Study Schedule Protocol I8R-JE-IGBJ

Study Schedule Protoco	Screening		Period 1	Wash out		Period 2	Follow-up/ED	Additional Follow-up for TE ADA ^a	Comments
Procedure	Days -28 to -2	Day -1	Day 1	3 to 14 days	Day -1	Day 1	Within 28±2 days after last study treatment		
Clinical Assessments									
Informed Consent	X								
Randomization			X						
Admission to CRU		X			X				Admission can be rescheduled if PG level is not 90 to 250 mg/dL on Day 1.

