Three clinical trials using LY900018 have been completed in non-Japanese adults with T1DM and T2DM: Study IGBC, Study I8R-MC-IGBA (IGBA), and an actual use study (Study I8R-MC-B002 [B002]). Studies IGBC and IGBA demonstrated comparable safety and efficacy between 3 mg LY900018 and 1 mg injectable glucagon in reversing insulin-induced hypoglycemia in adult patients with T1DM only (Study IGBA) or patients with T2DM and T1DM (IGBC). Study B002 was an actual use study that evaluated the effectiveness of 3 mg LY900018 administered by a trained caregiver to patients with T1DM experiencing moderate to severe hypoglycemia in a real-world environment of work and home. Study B002 demonstrated that 96% of moderate to severe hypoglycemic events were resolved within 30 minutes. Finally, 2 trials were conducted in pediatric patients with T1DM: Study I8R-MC-IGBB (IGBB) and Study I8R-MC-B001 (B001). Studies IGBB and B001 demonstrated effectiveness in rescuing pediatric patients from hypoglycemia.

All adult diabetic patients in the 2 inpatient clinical trials (Studies IGBA and IGBC) underwent hypoglycemia induction through IV insulin under close clinical supervision and were administered either LY900018 or injectable glucagon.

Patients fully recovered from hypoglycemia without additional actions to increase glucose level. Specifically, in Study IGBC, at 30 minutes after glucagon dosing, 98.7% (74 out of 75 patients) of LY900018 and 100% (75 out of 75) of IMG-treated patients achieved treatment success (defined as an increase in PG to \geq 70 mg/dL or an increase of \geq 20 mg/dL from nadir). The nadir is defined as the minimum glucose measurement at the time of or within 10 minutes following glucagon administration. The LY900018-treated patient who did not meet the above criteria did achieve both PG \geq 70 mg/dL and an increase of \geq 20 mg/dL from nadir at 40 minutes after dosing. Furthermore, the mean time to treatment success in participants with nadir glucose <50 mg/dL were 16 minutes in the LY900018 treatment arm and 13 minutes in the IMG treatment arm, respectively (Rickels et al. 2016).

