5.2. Number of Participants

Seventy five patients may be enrolled in order to have at least 66 patients (at least 30 patients with T1DM and T2DM, respectively) complete the study. For purposes of this study, a completer is defined as a patient who completes both periods with evaluable primary outcome. If patients discontinue from the study before completion of both periods with evaluable primary outcome for any reason, the patient may be replaced to ensure 66 patients complete the study. The replacement patients will be assigned the same treatment sequence as the patients to be replaced and will complete that treatment sequence in its entirety. Replacement should not occur beyond 75 patients enrolled, if it is expected to have at least 66 patients complete the study.

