5.4. Scientific Rationale for Study Design

This study design involves an open-label assessment of 3 mg LY900018 compared to 1 mg of the marketed IMG (GlucaGen). The study will be open label because the different administration routes (ie, intranasal and IM) cannot be blinded. The use of a crossover design allows each patient to serve as his or her own control, thereby reducing variability. The washout period of 3 to 14 days is considered sufficient based on the short half-life of LY900018 (t_{1/2} = approximately 25 minutes). Since the critical role of glucagon in the treatment of severe hypoglycemia is to raise the PG level sufficiently to restore cognition to the point where oral carbohydrate can be ingested, treatment success is defined either as an increase in PG returning to normal level of ≥70 mg/dL or an increase of ≥20 mg/dL from the PG nadir within 30 minutes after receiving glucagon, without the patient receiving additional actions to increase glucose. It is believed that an expected PG nadir of approximately 50 mg/dL (approximately 5 minutes after stop of insulin infusion at 60 mg/dL) is low enough to generate clinical symptoms in most participants and is high enough to avoid impairment of consciousness. The primary analysis includes both patients with T1DM and T2DM since it is expected that the proportion of treatment success is similar between patients with T1DM and T2DM.

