10.1. Sample Size Determination

Seventy five patients may be enrolled in order to have at least 66 patients (at least 30 patients with T1DM and T2DM, respectively) complete the study. For purposes of this study, a completer is defined as a patient who completes both periods with evaluable primary outcome. If patients discontinue from the study before completion of both periods with evaluable primary outcome for any reason, the patient may be replaced to ensure 66 patients complete the study. The replacement patients will be assigned the same treatment sequence as the patients to be replaced and will complete that treatment sequence in its entirety. Replacement should not occur beyond 75 patients enrolled, if it is expected to have at least 66 patients complete the study.

Assuming a non-inferiority margin (NIM) of 10%, a 98% treatment success rate for both treatment groups, and a within-patient correlation of zero, 66 completers will provide at least 90% power to show non-inferiority between LY900018 and IMG in treatment success from insulin-induced hypoglycemia with one-sided alpha level of 0.025 based on the Chi-square test.

The proposed NIM of 10% has been chosen based on the previously completed Phase 3 study (Rickels et al. 2016).

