10.3.1. Efficacy Analyses

10.3.1.1. Primary Efficacy Analysis

The primary objective is to demonstrate that 3 mg LY900018 is non-inferior to 1 mg IMG for the proportion (NIM=10%) of Japanese patients with T1DM or T2DM who achieve treatment success without receiving additional actions to increase the PG concentration. Treatment success is defined as either an increase in PG to \geq 70 mg/dL or an increase of \geq 20 mg/dL from PG nadir within 30 minutes after receiving study treatment. The nadir is defined as the minimum PG concentration at the time of or within 10 minutes following glucagon administration.

The primary analysis will be a treatment group comparison of the primary outcome. The percentage of treatment successes in each treatment group and the difference in percentages will be computed. A 2-sided 95% confidence interval (CI) will be obtained from the 1-sample mean of the paired differences in primary outcome (1=outcome observed; 0=outcome not observed) across 2 treatment visits. Non-inferiority of LY900018 will be declared if the upper limit of a 2-sided 95% CI constructed on the difference in percentages (IMG - LY900018) is less than the NIM of 10%.

Primary efficacy analysis will only include patients who complete both treatment visits with evaluable primary outcome. The following will be considered as non-evaluable primary efficacy outcomes and will be excluded from the analysis related to primary efficacy outcome:

- Patients with at least 1 treatment visit in which the lowest PG concentration at the time of or within 10 minutes following glucagon administration is ≥70 mg/dL;
- Patients who receive an external measure to raise PG concentration either before glucagon administration or within the first 10 minutes of glucagon administration.

Plasma glucose concentrations assessed through a central laboratory will be used to assess treatment success. Additional analysis will be performed if deemed necessary. The details will be provided in the SAP.

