9.3 Efficacy Assessment

9.3.1 Primary Efficacy Analysis

The primary outcome is the treatment success, which is defined as an increase in plasma glucose (PG) to \geq 70 mg/dL or an increase of \geq 20 mg/dL from PG nadir within 30 minutes after receiving glucagon, without receiving additional actions to increase the PG concentration. The nadir is defined as the minimum PG concentration at the time of or within 10 minutes following glucagon administration.

The primary analysis will be a treatment group comparison of the primary outcome in the EAS. The percentage of patients achieving treatment success in each treatment group and the difference in percentages will be computed. A 2-sided 95% CI will be obtained from the 1-sample mean of the paired differences in primary outcome (1 = outcome observed; 0 = outcome not observed) across 2 treatment visits. Noninferiority of nasal glucagon (NG) will be declared if the upper limit of a 2-sided 95% CI constructed on the difference in percentages (IMG minus NG) is less than the noninferiority margin of 10%. Specifically, for each patient, the paired difference of treatment success between IMG and NG will be calculated and PROC TTEST will be used to create the 95% CI of the mean difference.

Primary efficacy analysis will only include patients who complete both treatment visits with evaluable primary outcome. The analysis will be performed separately for each diabetes type. The following will be considered as nonevaluable primary efficacy outcome and excluded from the analysis related to primary efficacy outcome:

Final, 01 Feb 2018 Page 10 of 26

- Patients with at least 1 treatment visit in which the nadir PG is \geq 70 mg/dL;
- Patients receiving an external measure to raise PG concentration either before glucagon administration or within the first 10 minutes after glucagon administration.

Plasma glucose concentrations assessed through a central laboratory will be used to assess treatment success.

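### The primary t interval on paired 0/1 differences does not hold the stated one-sided alpha of 0.025: with IMG at 98% and LY900018 at the margin, its exact error is 4.9% at 66 completers

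*SAP*

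**What the plan says.** Protocol 10.3.1.1 defines the interval: "A 2-sided 95% confidence interval (CI) will be obtained from the 1-sample mean of the paired differences in primary outcome". The synopsis says the same. SAP 9.3.1 gives the implementation: "PROC TTEST will be used to create the 95% CI of the mean difference". Non-inferiority follows if the upper limit for IMG minus LY900018 is below 10%.

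The planning assumptions in the synopsis are 98% success on both treatments, a 10% margin, "One-sided alpha level of 0.025" and "A within-patient correlation of zero between 2 treatment visits". Protocol 10.1 and SAP 7 conclude that "66 completers will provide at least 90% power to show non-inferiority between LY900018 and IMG", and base this on a chi-square test. On numbers, protocol 5.2 says: "Seventy five patients may be enrolled in order to have at least 66 patients".

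The confirmatory comparison is pooled. Protocol 5.4 says: "The primary analysis includes both patients with T1DM and T2DM". SAP 9.3.1 adds an analysis by diabetes type, and SAP 11 declares no change from the protocol.

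SAP 9.3.2 reuses the primary method in further populations and adds a GEE Poisson model as a sensitivity analysis. Neither document gives the error rate of the t interval when success is close to 100%.

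**The concern.** Each paired difference can only be -1, 0 or 1. When nearly every patient succeeds on both treatments, both the mean and the standard error are set by a handful of discordant patients. If LY900018 is truly 10 points worse but few failures happen to occur, the estimate and its standard error both come out too small, and the upper limit slips under 10% too easily.

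The trial expects to operate in this region. Protocol 3.2 reports from the completed Phase 3 study that "98.7% (74 out of 75 patients) of LY900018 and 100% (75 out of 75) of IMG-treated patients achieved treatment success". At stake is whether the trial's only confirmatory claim carries the false-positive rate it states.

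**Working it through.** **Inputs.** Margin 0.10, one-sided alpha 0.025, success 98%, correlation 0 and 66 completers (synopsis, protocol 10.1, SAP 7); enrolment 75 (protocol 5.2); t interval and decision rule (SAP 9.3.1). The null point is derived, not printed: IMG 98% less the 10-point margin gives LY900018 88%.

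**The plan's own figure.** The variance of a paired difference at 98/98 is 2 × 0.98 × 0.02 = 0.0392. The normal-approximation sample size is (1.960 + 1.282)² × 0.0392 / 0.10² = 41.2. At n = 66 the standard error is √(0.0392/66) = 0.0244, and power is Φ(0.10/0.0244 − 1.960) = 98.4%. The exact power of the t rule is 96.3%, so the claim of at least 90% is met. That figure counts a trial with no discordant patient as a pass (interval 0 to 0), which has probability (1 − 0.0392)^66 = 7.1%.

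**Error of the t rule.** Let b be the number of patients who succeed on IMG only and c the number who succeed on LY900018 only. At 98/88 with zero correlation:

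- P(IMG only) = 0.98 × 0.12 = 0.1176
- P(LY900018 only) = 0.02 × 0.88 = 0.0176

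The upper limit is d + 1.997 × s/√66, with d = (b − c)/66 and s² = [(b + c) − 66d²]/65. For (b, c) = (3, 0), d = 0.0455 and s = 0.210, so the limit is 0.0455 + 1.997 × 0.0258 = 9.7%, a pass. For (4, 0) it is 12.0%, a fail. Summing the trinomial probabilities of all passing tables gives **4.87%**. A simulation of 400,000 trials gave 4.89%.

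| Completers | 66 | 67 | 68 | 69 | 70 | 71 | 72 | 73 | 74 | 75 |
|---|---|---|---|---|---|---|---|---|---|---|
| t-rule error at 98/88, % | 4.87 | 4.52 | 4.20 | 5.03 | 4.70 | 4.63 | 4.33 | 4.04 | 3.78 | 4.65 |

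**Other null points at n = 66.** The error is 6.4% at 99/89, 3.5% at 95/85 and 2.8% at 90/80. Correlation of 0.1, 0.2 and 0.3 at 98/88 gives 5.5%, 6.5% and 7.8%. If IMG never fails, the error is the binomial chance of at most 3 failures in 66 at 10%, which is 9.3%.

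**Where the excess lies.** The paired score statistic is (b − c − 6.6)/√(66[2q + 0.09]), where q is the restricted estimate of P(LY900018 only). The rule passes at −1.96 or below. With c = 0 and b of 1 to 3, q is 0 and the denominator is √5.94 = 2.437. So (1, 0) gives −2.30 and passes, while (2, 0) gives −1.89 and (3, 0) gives −1.48, and both fail.

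Seven tables pass the t rule and fail the score rule:

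| (b, c) | (2,0) | (3,0) | (3,1) | (3,2) | (4,3) | (5,5) | (8,10) |
|---|---|---|---|---|---|---|---|
| t upper limit, % | 7.3 | 9.7 | 9.1 | 8.3 | 9.6 | 9.6 | 9.9 |

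They carry 3.31 of the 4.87 points of error at 98/88 and 15.3 points of power at 98/98. Five tables with 28 or more discordant patients go the other way, with negligible probability.

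**Rules compared at n = 66.**

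| Rule | Error 98/88 | 99/89 | 100/90 | Power 98/98 |
|---|---|---|---|---|
| t, one-sided 0.025 | 4.9% | 6.4% | 9.3% | 96.3% |
| t, one-sided 0.01 | 2.3% | 2.6% | 3.3% | 89.6% |
| Adjusted Wald (Bonett-Price) | 3.6% | 4.0% | 3.3% | 93.3% |
| Paired score (Tango) | 1.6% | 1.3% | 0.8% | 81.1% |

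For each completer count from 66 to 75, take the largest error over IMG success of 95% to 100% and zero or positive correlation. It is 2.1% to 2.6% for the score rule and 3.0% to 6.7% for the t rule at 0.01.

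**The case against.** The plan expects 98% on both treatments, not 98/88. That is true, but type I error is defined at the margin, and 88% is the boundary once IMG is at its planned rate.

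About twice nominal is near the top of the range. Over 66 to 75 completers the ratio runs from 1.5 to 2, and the higher figures need a 99% or 100% IMG rate or positive correlation, which the plan does not assume. This stands as a limit on the size. Even so, every completer count in that range exceeds 2.5%.

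The practical effect is moderate. At n = 66 with IMG at 98%, the error is 3.0% if LY900018 is at 87% and 1.9% at 86%, so the rule behaves like a margin of 11 to 12 points. A result like the earlier study's, with one discordant patient, passes both rules (t limit 4.5%, score statistic −2.30). Both points are correct. But the disputed tables hold 15.3% of the probability under the plan's own assumptions, about one trial in seven.

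The score interval is conservative here and costs power. This also stands, and is why another interval is acceptable if its exact error is stated.

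SAP 9.3.1 speaks of analysis by diabetes type and does not itself say the pooled result carries the decision. The protocol does, and SAP 11 declares no change.

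**Conclusion.** The rule is fully specified, and it lacks a property the plan states for it. At IMG 98%, LY900018 88% and zero correlation, the one-sided error is 4.9% with 66 completers and 3.8% to 5.0% over 66 to 75, against 2.5%. The excess grows as IMG approaches 100% or correlation becomes positive, and it fades at lower success rates (2.8% at 90/80). Nothing in either document corrects it.

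The claim of at least 90% power is true for the t rule, but is obtained with this inflated error. The 96.3% takes the 0-to-0 interval as a pass, as the rule reads; if that outcome did not count, power would be 89.2%.

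The conclusion concerns the pooled comparison. It must be fixed, because it bears on the trial's only confirmatory claim.

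**What to change.** In SAP 9.3.1, protocol 10.3.1.1 and the synopsis, make the primary interval a paired score (Tango) 95% interval and keep the decision rule: upper limit for IMG minus LY900018 below 10%. Keep the t interval as a supportive display. Use the score interval wherever SAP 9.3.1 and 9.3.2 reuse the primary method.

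Restate power in protocol 10.1, the synopsis and SAP 7. For the score interval at 98/98 and zero correlation it is 81.1% at 66 completers, 88.9% at 69, 87.7% at 75 and 91.7% at 76. It therefore stays below 90% for every count from 66 to 75. At 66 it is about 91% if both rates are 99%, or if both are 98% with correlation 0.5.

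If the sponsor prefers another interval, state its exact error at 98/88, 99/89 and 100/90 for 66 to 75 completers. Moving the t interval to one-sided 0.01 is not enough: it gives 2.3% at 98/88 with 66 completers but 5.0% at 100/90 with 75. Part of the power loss is the score interval's conservatism. Among all rules monotone in the two discordant counts, the upper bound on power at 66 is 90.5% if 2.5% is held at 98/88 alone. If it is held for IMG success from 95% to 100%, the bound is 88.0% at 66, 90.6% at 70 and 92.6% at 75.

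The change itself is wording and a few lines of code, with no new data. The real cost is either accepting lower power at 98/98 or enrolling more patients. SAP 3 requires sign-off before the first dose and the trial is open-label (protocol 7.3), so a later change needs a dated amendment made before outcome data are reviewed. The sponsor must decide under protocol 10.3 whether the interval is a principal feature that requires a protocol amendment.

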3. INTRODUCTION

This SAP has been developed after review of the Clinical Study Protocol (final version dated 26 October 2017 and protocol amendment (a) (final version dated 05 December 2017).

This SAP describes the planned analysis of the safety, tolerability and pharmacokinetic (PK) and pharmacodynamic (PD) data from this study. A detailed description of the planned TFLs to be presented in the clinical study report (CSR) is provided in the accompanying TFL shell document.

The intent of this document is to provide guidance for the statistical and PK analyses of data. In general, the analyses are based on information from the protocol, unless they have been modified by agreement between Eli Lilly and Company and Covance Early Clinical (EC) Biometrics. A limited amount of information concerning this study (e.g., objectives, study design) is given to help the reader's interpretation. This SAP must be signed off prior to first subject administration for this study. When the SAP and TFL shells are agreed upon and finalized, they will serve as the template for this study's CSR.

This SAP supersedes the statistical considerations identified in the protocol; where considerations are substantially different, they will be so identified. If additional analyses are required to supplement the planned analyses described in this SAP, they may be performed and will be identified in the CSR. Any substantial deviations from this SAP will be agreed upon between Eli Lilly and Company and Covance EC Biometrics and identified in the CSR. Any minor deviations from the TFLs may not be documented in the CSR.

This SAP is written with consideration of the recommendations outlined in the International Council on Harmonisation (ICH) E9 Guideline entitled Guidance for Industry: Statistical Principles for Clinical Trials¹ and the ICH E3 Guideline entitled Guidance for Industry: Structure and Content of Clinical Study Reports².

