7. SAMPLE SIZE JUSTIFICATION

Seventy five patients may be enrolled in order to have at least 66 patients (at least 30 patients with T1DM and T2DM, respectively) complete the study. For purposes of this study, a completer is defined as a patient who completes both periods with evaluable primary outcome. If patients discontinue from the study before completion of both periods with evaluable primary outcome for any reason, the patient may be replaced to ensure 66 patients complete the study. The replacement patients will be assigned the same treatment sequence as the patients to be replaced and will complete that treatment sequence in its entirety. Replacement should not occur beyond 75 patients enrolled, if it is expected to have at least 66 patients complete the study.

Assuming a non-inferiority margin (NIM) of 10%, a 98% treatment success rate for both treatment groups, and a within-patient correlation of zero, 66 completers will provide at least 90% power to show non-inferiority between LY900018 and IMG in treatment success from insulin-induced hypoglycemia with one-sided alpha level of 0.025 based on the Chi-square test.

The proposed NIM of 10% has been chosen based on the previously completed Phase 3 study (Rickels et al. 2016)³.

Final, 01 Feb 2018 Page 8 of 26

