11. CHANGES FROM THE PROTOCOL SPECIFIED STATISTICAL ANALYSES

There were no changes from the protocol specified statistical analyses.

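### SAP 9.3.1 says the primary analysis is run separately by diabetes type, which conflicts with the single pooled non-inferiority test that the protocol defines and the sample size supports

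*SAP*

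**What the plan says.** **Protocol.** The synopsis (Section 1, Statistical Analysis) describes one pooled comparison: "The primary analysis will be a treatment comparison of the percentage of patients, including both T1DM and T2DM, who achieve treatment success". Section 5.4 gives the reason: "The primary analysis includes both patients with T1DM and T2DM since it is expected that the proportion of treatment success is similar" in the two types. Section 10.3.1.1 has one comparison, one 95% confidence interval and one declaration rule (upper limit for IMG minus LY900018 below 10%). It contains no split by type.

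**SAP 9.3.1.** This section starts the same way: "The primary analysis will be a treatment group comparison of the primary outcome in the EAS". The EAS, as defined in SAP 8, is not restricted by diabetes type. The same single interval and 10% rule follow, then a sentence shared with Protocol 10.3.1.1: "Primary efficacy analysis will only include patients who complete both treatment visits with evaluable primary outcome". Directly after it the SAP inserts a sentence that the protocol does not have: "The analysis will be performed separately for each diabetes type".

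**Elsewhere in the SAP.**
- Section 7 keeps the pooled sizing: "66 completers will provide at least 90% power to show non-inferiority between LY900018 and IMG in treatment success from insulin-induced hypoglycemia". The only condition on the mix is at least 30 completers of each type.
- Section 3 sets precedence: "This SAP supersedes the statistical considerations identified in the protocol; where considerations are substantially different, they will be so identified".
- Section 11 reports: "There were no changes from the protocol specified statistical analyses".
- Sections 9.4.2 (PK) and 9.5.2 (PD) specify analysis by type and overall.

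**The concern.** In its position, the inserted sentence refers to the primary efficacy analysis. It does not say that the by-type analyses come in addition to a pooled one, or that they are supportive. Read literally, it turns one confirmatory test on 66 pairs into two tests on 30 to 36 pairs each. It gives no rule for combining them: the SAP does not say whether both types must pass or whether one is enough.

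The protocol cannot simply be used to overrule the sentence, because the SAP states that it supersedes the protocol's statistical considerations. Nor can the sentence be treated as a declared change, because Section 11 declares none.

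The point at stake is which test carries the non-inferiority claim. This is an open-label trial, and if the text stays as it is, a pooled verdict and by-type verdicts could each be defended from the SAP after the data are seen. SAP 9.3.2 inherits the problem, because it compares further populations by diabetes type with the method of 9.3.1.

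**Working it through.** **Inputs** (Protocol 1 and 10.1; SAP 7 and 9.3.1)
- Success 98% on both treatments, within-patient correlation 0, margin 10 percentage points, one-sided alpha 0.025.
- 66 completers with at least 30 of each type, so at exactly 66 the split runs from 30/36 to 33/33.
- Method: t interval on the mean of the paired differences D = IMG − LY900018. Non-inferiority is declared if mean + t(0.975, n−1) × SD/√n < 0.10.

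**Step 1: the plan's own figure.** With correlation 0, Var(D) = 2 × 0.98 × 0.02 = 0.0392. At n = 66 the standard error is √(0.0392/66) = 0.02437. Normal-approximation power is Φ(0.10/0.02437 − 1.96) = 98.4%. The stated figure of at least 90% is met.

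**Step 2: exact power of the planned interval.** The number of patients succeeding only on IMG (i) and the number succeeding only on LY900018 (j) follow a trinomial distribution. Each cell has probability 0.98 × 0.02 = 0.0196, and the remaining probability is 0.9608. I summed the probabilities of all (i, j) that meet the rule. If i = j = 0 the interval has zero width. The SAP does not say how that case is handled, so both conventions are shown.

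| Pairs | Exact power, zero width = pass | Exact power, zero width = not a pass |
|---|---|---|
| 66 (pooled) | 96.3% | 89.2% |
| 36 | 84.7% | 61.0% |
| 35 | 85.1% | 60.4% |
| 34 | 85.7% | 60.1% |
| 33 | 86.4% | 59.7% |
| 32 | 87.1% | 59.3% |
| 31 | 87.7% | 58.8% |
| 30 | 69.9% | 39.8% |

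No by-type test reaches 90%. The normal approximation agrees on that: 79.0% at 30 pairs, 82.7% at 33 and 85.8% at 36.

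**Step 3: how many failures each test tolerates.** Take patients who fail only on LY900018, with none failing only on IMG.
- n = 30, one patient: mean = 1/30 = 0.0333 and SE = 0.0333, so the upper limit is 0.0333 × (1 + 2.045) = 10.15%, a fail.
- n = 31, one patient: 3.042/31 = 9.81%, a pass. This explains the drop in power at n = 30.
- Two patients: 16.14% at n = 30 and 13.42% at n = 36, a fail at every size in the range.
- n = 66, three patients: 0.0455 + 1.997 × 0.0258 = 9.71%, a pass. Four patients give 11.97%, a fail.

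**Step 4: how often the readings disagree** (98%/98%, zero width = pass).

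| Split | Both types pass | Pooled passes, at least one type fails | Pooled fails, at least one type passes |
|---|---|---|---|
| 30/36 | 59.2% | 37.1% | 1.4% |
| 31/35 | 74.6% | 21.7% | 2.0% |
| 32/34 | 74.6% | 21.7% | 2.0% |
| 33/33 | 74.7% | 21.7% | 2.0% |

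**Step 5: error rate if either type could carry the claim.** The documents state no such rule; it is shown only because the text does not exclude it. Under 98% on IMG and 88% on LY900018, a true difference equal to the margin, the single-test false-positive rates are 6.49% at n = 30 and 6.79% at n = 36. At least one type then passes with probability 1 − (1 − 0.0649)(1 − 0.0679) = 12.8%. The same calculation gives 17.1% at 31/35, 16.8% at 32/34 and 16.7% at 33/33. The pooled t interval gives 4.9%, already above the nominal 2.5%; that excess belongs to the interval method, not to this sentence.

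**The case against.** The best defence is that a pooled test with extra by-type reporting was plainly meant.
- SAP 9.1 lists the proportion of treatment success among the results to be reported by diabetes type, next to demographics and adverse events. The sentence in 9.3.1 may only apply that convention.
- SAP 9.2 also asks for outputs by type without mentioning overall results, and nobody would conclude that overall demographics were dropped.
- The Poisson sensitivity analysis in SAP 9.3.2 is run on the EAS with no split and no diabetes-type term.
- SAP 7 keeps the pooled sizing. Section 3 promises that substantial departures will be identified, and Section 11 identifies none. Protocol 10.3 requires an amendment when an analysis change alters a principal feature of the protocol.

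On size, the defence notes that disagreement at the planned rates is almost one-sided: a by-type pass after a pooled failure has a probability of only 1.4% to 2.0%, and both types never pass when the pooled test fails. The value at n = 30 is a discreteness effect at one split.

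Most of this stands as evidence of intent, and I accept that a pooled test was probably intended. The limited scope for rescuing a failed trial at the planned rates also stands. What does not follow is that the text is settled. Because SAP 9.1 already required by-type reporting, the added sentence was not needed for that purpose, and it sits unqualified in the section that holds the decision rule. No passage states which result decides. Setting n = 30 aside still leaves 22% of trials with a pooled pass and a failing type.

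**Conclusion.** The concern holds, and the text must be corrected. SAP 9.3.1 contradicts the protocol's pooled primary analysis and its own opening sentence. Followed literally, it replaces a test with 96.3% exact power by by-type tests with 70% to 88%, and by 59% to 75% if both types must pass. The pooled and by-type readings would give a pooled pass with at least one failing type in 22% to 37% of trials.

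These figures assume exactly 66 completers, 98% success on both treatments in each type, zero correlation, and zero-width intervals counted as a pass. If zero-width intervals are not counted as a pass, the by-type tests fall to 40% to 61% and the pooled test to 89.2%. The finding is that the governing text leaves the deciding test unresolved; it is not that the sponsor has dropped the pooled test.

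**What to change.** In SAP 9.3.1, replace the by-type sentence with wording such as: *The confirmatory non-inferiority test is one test on the pooled EAS (T1DM and T2DM combined). Results by diabetes type are also presented with confidence intervals as supportive and carry no non-inferiority decision.*

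In SAP 9.3.2, keep the populations already listed (ARS; EAS patients with nadir below 50 mg/dL on both visits). Add that these comparisons are made overall and also by diabetes type, as supportive analyses without a non-inferiority decision.

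The cost is two sentences in the SAP, with no change to the protocol, sample size or data collection. The statement of no changes in SAP 11 then becomes true on this point.

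If separate confirmatory tests by type were really intended, this edit would not be enough. The SAP would need a stated decision rule, an entry in Section 11 and a new sample-size justification. By the normal approximation that is 42 pairs per type for 90% power in each, or 51 per type for 90% power that both pass.
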